## 5.3 Exclusion criteria

Patients eligible for this study must not meet **any** of the following criteria:

1. Patients with symptomatic central nervous system (CNS) metastases who are neurologically unstable or require increasing doses of steroids or local CNS-directed therapy (such as radiotherapy, surgery or intrathecal chemotherapy) to control their CNS disease.

2. Patients with clinically significant, uncontrolled heart disease or corrected QT (QTc) interval > 480 milliseconds, using the Fridericia correction (QTcF).
3. Patients with the following laboratory values during screening:
  - Creatinine > 1.5 x ULN for age.
  - Total bilirubin > 1.5 x ULN for age, except for patients with Gilbert's syndrome, who may be included if total bilirubin is  $\leq 3.0$  x ULN and direct bilirubin is  $\leq 1.5$  x ULN.
  - Alanine aminotransferase (ALT) > 3 x ULN for age, except for patients that have tumor involvement of the liver, who must have a value  $\leq 5$  x ULN.
  - Serum aspartate aminotransferase (AST) > 3 x ULN for age, except for patients that have tumor involvement of the liver, who must have a value  $\leq 5$  x ULN.
  - Absolute neutrophil count (ANC) <  $0.75 \times 10^9/L$  without use of granulocyte growth factor for  $\geq 14$  days.
  - Platelet count <  $50 \times 10^9/L$ .
  - Hemoglobin (Hgb) < 8 g/dL.
  - Alkaline phosphatase (ALP) > 5.0 x ULN
  - Serum amylase > 2 x ULN
  - Serum lipase > ULN
  - Fasting plasma glucose  $\geq 175$  mg/dL ( $\geq 9.8$  mmol/L)
  - Potassium, magnesium, calcium or phosphate abnormality > CTCAE grade 1.
4. Body surface area (BSA) <  $0.35 \text{ m}^2$ .
5. Impairment of gastrointestinal (GI) function or GI disease that may significantly alter the absorption of LDK378 (e.g., ulcerative diseases, uncontrolled nausea, vomiting, diarrhea, or malabsorption syndrome).
6. Evidence of active viral hepatitis, including Hepatitis A, B or C (testing for viral hepatitis is not mandatory).
7. Known diagnosis of human immunodeficiency virus (HIV) infection (HIV testing is not mandatory).
8. Presence of  $\geq$  CTCAE grade 2 toxicity (except alopecia, peripheral neuropathy, ototoxicity and lymphopenia, which are not excluded if grade 3 or less) due to prior cancer therapy.

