**Table 6-2 Criteria for defining dose-limiting toxicities**

**Any adverse event of CTCAE grade 3 or higher during cycle 1 is a DLT, with the following exceptions**

|            |  |
|------------|--|
| Hematology | 
 
• Neutropenia is a DLT if it is CTCAE grade 4 lasting > 7 days
 
• Thrombocytopenia is a DLT if it is CTCAE grade 3 lasting > 7 days or CTCAE grade 4 thrombocytopenia at any time
 
• Anemia is a DLT if it is CTCAE grade 4 lasting > 7 days
 
• Lymphopenia is a DLT if it is CTCAE grade 4
 
 |
| Renal      | 
 
• Serum creatinine > 2 x ULN is a DLT Refer to Table 6-5 for additional follow up.
 
  |
| Hepatic    | 
 
• AST or ALT increase is a DLT if CTCAE grade 3 or greater
 
• Total bilirubin is CTCAE grade 2 with AST or ALT CTCAE grade 1 in the absence of cholestasis or hemolysis. Refer to Table 6-5 for additional follow up.
 
  |
| Pulmonary  | 
 
• Pneumonitis or ILD of any grade without infectious etiology is a DLT
 
   |

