## Dose modification related to DLTs

If a patient experiences a DLT, treatment with LDK378 should be held. Following resolution of the toxicity to grade 1 or to the patient's baseline value the patient may resume treatment with LDK378. In general patients who resume therapy following a DLT should resume at a lower dose level assessed to be safe with a minimum dose reduction of 50 mg. However, following recovery of a DLT that was not considered clinically important or can be managed if it recurs (e.g., replacement of an electrolyte), the patient may resume therapy without dose reduction, if the investigator considers that to be in the best interest of the patient. The dose should not be reduced below 150 mg/m^2. Provisional dose levels for LDK378 are listed in [Table 6-1](#).

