### 6.3 Dose modifications

#### 6.3.1 Dose modification and dose delay

For patients who do not tolerate the protocol-specified dosing schedule, dose adjustments are permitted in order to allow the patients to continue the study treatment. Any changes in LDK378 administration must be recorded on the Dosage Administration Record eCRF.

Patients whose treatment is interrupted or permanently discontinued due to an AE must be followed until resolution or stabilization of the event. Patients requiring interruptions greater than 2 cycles (42 days) will be discontinued from study treatment. In certain cases, if the Investigator and the Sponsor conclude that a patient, who has experienced a treatment

interruption greater than 2 cycles (42 days), could benefit from additional treatment, continuation may be allowed.

LDK378 dose reduction will follow the dose reduction steps described in [Table 6-3](#). For each patient, a maximum of 3 dose modifications will be allowed after which the patient must be discontinued from treatment with LDK378. Once the dose of LDK378 has been reduced, it cannot be re-escalated. If a patient continues treatment with LDK378 after RECIST-defined PD confirmed by the investigator, the criteria for dose modification will also apply.

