| Grade 4 (> 10.0 x ULN)  | Permanently discontinue patient from LDK378   |
| AST or ALT   |   |
| Grade 1 (> ULN and ≤ 3.0 x ULN)   | Maintain dose level with LFTs*** monitored per protocol   |
| Grade 2 (> 3.0 and ≤ 5.0 x ULN) without total bilirubin elevation to > 2.0 x ULN  | Maintain dose level with LFTs*** monitored per protocol   |
| Grade 3 (> 5.0 and ≤ 20.0 x ULN) without total bilirubin elevation to > 2.0 x ULN   | Omit dose until resolved to ≤ Grade 1, then ↓ 1 dose level  |
| Grade 4 (> 20.0 x ULN) without total bilirubin elevation to > 2.0 x ULN   | Omit dose until resolved to ≤ Grade 1, then ↓ 1 dose level  |
| AST or ALT and concurrent Total bilirubin  |   |
| AST or ALT > 3.0 x ULN with total bilirubin > 2.0 x ULN in the absence of cholestasis or hemolysis  | Permanently discontinue patient from LDK378. Refer to Section 6.3.2.2 for additional follow-up.                                     |
| AST or ALT > 5.0 and ≤ 20.0 x ULN with total bilirubin > 1.5 and ≤ 3.0 x ULN  | Permanently discontinue patient from LDK378 if event reoccurs after dose reduction.   |
| PANCREATIC   |   |
| Amylase and/or lipase evaluations (in absence of clinical symptoms)   |   |
| Grade 1 (> ULN and ≤ 1.5 x ULN)   | Maintain dose level   |
| Grade 2 (> 1.5 - 2.0 x ULN)   | Maintain dose level   |
| Grade ≥ 3 (> 2.0 x ULN)   | Omit dose until resolved to ≤ Grade 1, then ↓ 1 dose level  |
| Note: Withhold LDK378 for acute onset of new or progressive unexplained abdominal symptoms, such as severe pain or vomiting; perform diagnostic procedures (e.g., abdominal CT scan or ultrasound) to exclude pancreatic pathology. |   |
| RENAL  |   |

| Worst toxicity (CTCAE 4.03 Grade)*               | Dose Modifications for LDK378  |
|---|---|
| Serum creatinine                                 |   |
| Grade 1 (>1 and ≤1.5 x baseline; >ULN and ≤ 1.5 x ULN)  | Maintain dose level   |
| Grade 2 (>1.5 and ≤3.0 x baseline; > 1.5 and ≤ 3 x ULN) | Omit dose until resolved to ≤ Grade 1, then:
If resolved in ≤ 7 days, then maintain dose level
If resolved in > 7 days, then ↓ 1 dose level                         |
| Grade 3 (>3.0 x baseline; > 3.0 and ≤ 6.0 x ULN)        | Omit dose until resolved to ≤ Grade 1, then ↓ 1 dose level  |
| Grade 4 (> 6.0 x ULN)                                   | Permanently discontinue patient from LDK378   |
| GASTROINTESTINAL                                 |   |

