| 
 
Withhold LDK378 for acute onset of new or progressive unexplained pulmonary symptoms, such as dyspnea, cough and fever and during diagnostic workup for pneumonitis/ILD.
 
During evaluation of potential grade 2, 3, and 4 pneumonitis, if an infectious etiology is confirmed (i.e., pneumonia) and pneumonitis is excluded, then consider resuming LDK378 at current dose level after the pneumonia resolves.
 
For pneumonitis not treatment related: If pneumonitis/ILD of grade 2 or worse is confirmed, study drug should be permanently discontinued. If Grade 1 resolves within 6 weeks, LDK378 may be resumed reduced by 1 dose level, otherwise it must be discontinued. If grade 1 pneumonitis recurs after dose reduction, then LDK378 must be permanently discontinued.
 
 |   |
| PNEUMONITIS  |   |
| Any Grade treatment-related ILD/pneumonitis   | Permanently discontinue patient from LDK378   |
| CARDIAC  |   |
| Electrocardiogram QT corrected (QTc) interval prolonged  |   |
| Grade 1 (QTc 450-480 ms)
Grade 2 (QTc 481-500 ms)  | Maintain dose level   |

| Worst toxicity (CTCAE 4.03 Grade)*   | Dose Modifications for LDK378  |
|---|---|
| Grade 3 (QTc $\geq$ 501 ms on at least two separate ECGs)   | 
Omit dose until QTc is less than 481 ms , then <math>\downarrow</math> 1 dose level
                     - Assess the quality of the ECG recording and the QT value and repeat if needed
 
Repeat ECG in 24 hours, or less, as clinically indicated; continue monitoring as clinically indicated until QTc < 481 ms.
 
In addition:-Determine the serum electrolyte levels (in particular hypokalemia, hypomagnesemia). If abnormal, correct abnormalities before resuming study drug treatment
 
- Review concomitant medication use for drugs with the potential to increase the risk of drug exposure related to QT prolongation
 
After resumption of dosing:
                     - Repeat ECGs 7 days after dose resumption for all patients who had therapy interrupted due to QTc <math>\geq</math> 501 ms.
 |
| Grade 4 (QTc $\geq$ 501 or > 60 ms change from baseline and Torsades de pointes or polymorphic ventricular tachycardia or signs/symptoms of serious arrhythmia) | Permanently discontinue patient from LDK378   |
| BRADYCARDIA  |   |

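### For several events that are DLTs, Protocol section 6.2.4 and Table 6-4 give different stop, restart, hold and dose-floor instructions, and no section says which governs

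*Protocol*

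**What the plan says.** Section 6.2.4 sets a single rule for every DLT. "If a patient experiences a DLT, treatment with LDK378 should be held." Restart requires recovery to grade 1 or baseline: "baseline value the patient may resume treatment with LDK378. In general patients who resume therapy following a DLT should resume at a lower dose level". The cut is at least 50 mg. Restart may be at the same dose if the DLT was not clinically important or can be managed, with electrolyte replacement as the example. The floor is 150 mg/m². The text points to Table 6-1 for dose levels and does not mention Table 6-4.

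Table 6-2 decides what counts as a DLT: any grade 3 or higher event in cycle 1, with listed variations, among them "Pneumonitis or ILD of any grade without infectious etiology is a DLT".

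Section 6.3.1 and Table 6-4 then rule event by event. The row "Any Grade treatment-related ILD/pneumonitis" leads to permanent discontinuation. For isolated grade 3 or 4 AST/ALT the instruction is "Omit dose until resolved to ≤ Grade 1, then ↓ 1 dose level". The note under Table 6-3 sets a floor of 200 mg/m²/day and discontinues patients who would need less. Section 6.3.1 adds: "Patients requiring interruptions greater than 2 cycles (42 days) will be discontinued from study treatment". Its next sentence lets the investigator and sponsor agree to continue.

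Exclusion criterion 3 bars AST/ALT above 3 x ULN, "except for patients that have tumor involvement of the liver, who must have a value" of at most 5 x ULN. It admits an ANC from 0.75 x 10⁹/L.

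**The concern.** One cycle 1 event can fall under two instructions that cannot both be followed. The sharpest case is treatment-related pneumonitis/ILD, for which sections 1.2.1.2.1 and 2.6 acknowledge fatal cases: one text permits restart, the other ends treatment.

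The analysis is also affected. SAP section 2.3 tabulates protocol deviations, including patients not withdrawn as the protocol requires and treatment deviations. SAP section 2.8.1 tabulates adverse events associated with discontinuation. Protocol section 7.2.2 measures tolerability by events leading to delay or discontinuation. Without a governing rule, the same conduct can be classed as compliant or as a deviation.

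**Working it through.** No sample size or probability is involved. The check matches each DLT in Table 6-2 with its row in Table 6-4 and compares both with section 6.2.4.

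| Event (DLT under Table 6-2) | Section 6.2.4 | Section 6.3.1, Tables 6-3 and 6-4 |
|---|---|---|
| (a) Treatment-related pneumonitis/ILD, any grade | Hold; may resume at grade 1 or baseline | Permanent stop |
| (a) Creatinine grade 4 (> 6 x ULN) | same | Permanent stop |
| (a) QTc grade 4 | same | Permanent stop |
| (a) AST/ALT > 3 x ULN with bilirubin > 2 x ULN, no cholestasis or hemolysis | same | Permanent stop |
| (a) Bilirubin grade 4 (> 10 x ULN) | same | Permanent stop, unless indirect only with hemolysis excluded (footnote) |
| (b) Thrombocytopenia grade 4, or grade 3 for > 7 days | same | Restart at grade 2 or better |
| (b) Neutropenia grade 4 for > 7 days | same | Restart at grade 2 or better |
| (b) Fatigue grade 3 for > 7 days | same | Restart at grade 2 or better |
| (b) AST/ALT grade 3 or 4, isolated | same | Restart at grade 1; baseline not mentioned |
| (c) Hypophosphatemia grade ≥ 3 for > 7 days | same | Maintain dose, supplement |
| (c) Nausea grade 2 despite optimal anti-emetics | same | Maintain dose, adjust anti-emetic |
| (d) Dose floor | 150 mg/m² | 200 mg/m²/day |

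**Group (a).** A DLT is by definition not attributed to disease, intercurrent illness or other therapy, so DLT pneumonitis largely coincides with the treatment-related row. A grade 1 case is already at the 6.2.4 restart grade when it occurs. The combined AST/ALT and bilirubin event is a DLT at least when AST/ALT is grade 3 or higher. Two narrower rows follow the same pattern: grade 3 bilirubin with AST/ALT at most 3 x ULN that takes more than 7 days to resolve (same footnote), and grade 4 bradycardia without a contributing concomitant drug.

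**Group (b).** On the Table 6-4 scale, a patient with normal entry counts restarts at platelets of 50 x 10⁹/L under Table 6-4 but 75 under 6.2.4. For ANC the levels are 1.0 and 1.5. Abnormal entry values can reverse the order. Two illustrations with assumed values:

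- ANC 0.8 at entry, 0.4 for more than 7 days, then back to 0.8. Section 6.2.4 is met (baseline); Table 6-4 is not (0.8 < 1.0).
- ALT 4 x ULN at entry with liver involvement, 8 x ULN in cycle 1 (grade 3), then stable at 4 x ULN. Section 6.2.4 is met (baseline); Table 6-4 is not (4 > 3). After 42 days the default is discontinuation, which investigator and sponsor can waive.

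**Group (c).** The electrolyte example in 6.2.4 relaxes the dose at restart. It does not remove the hold, so holding and maintaining remain incompatible.

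**Group (d).** A reduction to between 150 and 200 mg/m² is allowed by one text; under the other it means permanent discontinuation.

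**Precedence.** Table 6-4 is not limited to non-DLT events or to later cycles, and 6.3.1 gives its own rule for a DLT of QTc prolongation. Scope therefore does not separate the sections, and no sentence ranks them.

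**The case against.** The best defence is that the specific table prevails over a general permission. Section 6.2.4 says only that a patient may resume, and several places lead the reader to section 6.3.1 or Table 6-4. Section 6.3.1 takes up QTc DLTs and stops grade 4. Section 6.3.2.4 sends pneumonitis to Table 6-4. Sections 6.3.2.5 and 6.3.2.6 do the same for diarrhea, nausea and vomiting. Table 6-2 refers hepatic and renal DLTs to Table 6-5, whose note refers on to Table 6-4. Section 6.3.2.7 allows the dose to be maintained in hypophosphatemia.

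Much of this stands for group (a): a permission to restart need not cancel an instruction to stop. But none of these places says that it overrides 6.2.4, whose passage is itself the one headed for DLTs. Nor does the argument settle the cytopenias and fatigue, where the table restarts at a grade that 6.2.4 does not accept, or the hold in hypophosphatemia, or the two floors.

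It is also fair that DLTs occur only in the first 21 days, and that the Amendment 8 rationale reports recruitment complete, twelve patients still on treatment, and at least 6 cycles completed by all patients. No new DLT is then expected.

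**Conclusion.** The contradiction is real for the listed events. It comprises five stop-versus-restart events (plus two narrower rows), three restart grades, the missing baseline alternative for AST/ALT, two hold-versus-maintain events and the dose floor. This rests on reading 6.2.4 as written, as applying to every DLT, and on the absence of any ranking sentence.

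A reader might infer more than the documents support:

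- That every DLT is affected. For amylase/lipase grade 3 or higher and for grade 3–4 diarrhea and vomiting, both texts use grade 1 as the recovery grade. For isolated AST/ALT only the baseline alternative differs.
- That a child admitted with abnormal values must be stopped at 42 days. That is the default, not automatic.
- That grade 4 bilirubin always ends treatment under Table 6-4. The indirect-only footnote says otherwise.
- That the MTD estimate is affected. Table 6-2 defines a DLT whatever happens afterwards. The dose-determining set refers to patients who discontinue because of a DLT, which reads awkwardly for a restarted patient with fewer than 16 doses. However, section 6.2.3 and SAP Table 5-1 keep any patient with a DLT evaluable, and no effect on the model is shown.

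The prospective effect is small. What remains is how cycle 1 conduct, deviations and discontinuations are judged in the final analysis, and the later medically significant events that 6.2.4 says should be followed up as for DLTs.

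**What to change.** Reconcile section 6.2.4, section 6.3.1 with Tables 6-3 and 6-4, and exclusion criterion 3. State which section governs when a DLT is also a Table 6-4 event. Give one restart condition per event in both places, saying whether baseline counts for patients admitted with abnormal values. State one dose floor. Which clinical rule applies is for the sponsor and investigators to decide.

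For the final analysis, record before database lock which rule is used to classify cycle 1 restarts and discontinuations as deviations.

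The cost is a wording change and a site notification, with no extra procedures or patients.

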**Table 6-1 Provisional dose levels for fasted pediatric dose escalationa**

| Dose Level        | Provisional Daily Dose b | Increment from previous dose |
|-------------------|-------------------------------------|------------------------------|
| -1 c   | 200 mg/m                | 33% reduction                |
| 1 (starting dose) | 300 mg/m                | Starting dose                |
| 2                 | 450 mg/m                | 50% increase                 |
| 3                 | 560 mg/m                | 25% increase                 |
| 4                 | 700 mg/m                | 25% increase                 |
| 5                 | 875 mg/m                | 25% increase                 |
| 6                 | 1090 mg/m               | 25% increase                 |

a. This table is intended as an example for guidance for the dose escalation part only. Intermediate or higher dose levels may be used if the dose-escalation rules presented in this protocol are followed. Actual dose levels will be confirmed in writing by Novartis and provided to all participating study sites before treatment of patients in a new cohort.

b. All doses will be dosed on a mg/m^2 basis, rounded to the nearest 50 mg (refer to Section 6.1.1 for details).

c. Dose level -1 may be used if appropriate (e.g., if the starting dose level is not well tolerated).

The fasted dose escalation will continue until the MTD and/or the RDE dose is reached. Following completion of the dose escalation part of the study, a dose will be chosen for the expansion part of the study. The dose for the expansion part will be opened at either the fasted MTD, or a lower dose that is determined to be the RDE.

After the fasted dose escalation has reached the MTD and/or RDE, the fed dose escalation will begin. The starting dose for the fed dose escalation part will be approximately 63% of the fasted MTD determined in this study. This is based on the data from adult healthy volunteers

taking LDK378 with a low-fat meal. It is estimated that the steady state exposure of LDK378 with a low-fat meal will be increased 1.58 fold. Dose escalations during the fed dose escalation part of the study will be limited to a 25% or smaller increase above the prior fed dose level.

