**Table 6-3 Dose reduction steps for LDK378 at RDE (fasted and fed states)**

| LDK378 dose levels  | Dose* and schedule                             |
|---------------------|--|
| Starting dose level | RDE: 500/510 mg/m  QD continuously |
| Dose level -1       | 400 mg/m  QD continuously          |
| Dose level - 2      | 300 mg/m  QD continuously          |
| Dose level -3       | 200 mg/m  QD continuously          |

\*Dose reduction should be based on the worst preceding toxicity as per NCI-CTCAE version 4.03

\*\*Dose reduction below 200 mg/m^2/day is not allowed. If a dose reduction below 200 mg/m^2/day is required, the patient should be permanently discontinued from LDK378

Guidelines for dose interruptions and re-initiation of LDK378 treatment (with or without dose reduction) are described in [Table 6-4](#).

Patients, who discontinue from the study for a study-related adverse event or an abnormal laboratory value, must be followed as described in [Section 7.1.3](#).

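### Section 6.2.4 points to Table 6-1 for dose levels after a DLT and Section 6.3.1 to Table 6-3 for all reductions; the two tables and their floors differ, and neither defines a dose level for every assigned dose

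*Protocol*

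**What the plan says.** Protocol Section 6.2.4, under the heading on dose modification related to DLTs, says that patients who resume after a DLT in general "should resume at a lower dose level assessed to be safe with a minimum dose reduction of 50 mg". It sets a floor of 150 mg/m2 and adds that "Provisional dose levels for LDK378 are listed in" Table 6-1. It also allows resumption without any reduction after a DLT that was not clinically important or is manageable if it recurs.

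Table 6-1 is titled "Provisional dose levels for fasted pediatric dose escalation". Its levels are 200, 300, 450, 560, 700, 875 and 1090 mg/m2. Its footnote reads: "This table is intended as an example for guidance for the dose escalation part only". The footnote also permits intermediate levels.

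Section 6.3.1 says "LDK378 dose reduction will follow the dose reduction steps described in" Table 6-3 and makes no exception for DLTs. Table 6-3 is headed "Dose reduction steps for LDK378 at RDE (fasted and fed states)". Its only starting row is the RDE, 500/510 mg/m2, followed by 400, 300 and 200. Its footnote forbids reduction below 200 mg/m2 and requires permanent discontinuation if a lower dose would be needed.

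Many rows of Table 6-4 call for a reduction of one dose level. The Section 6.3.1 paragraph on a DLT of QTc prolongation requires at least one dose level and at least 50 mg. Neither is limited to patients who started at the RDE. SAP Table 2-1 lists the dose levels as 200, 300, 450, 510 and 560 mg/m2 fasted and 320, 400 and 500 mg/m2 fed.

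**The concern.** A DLT falls under both sections. Section 6.2.4 addresses it directly and names one table. Section 6.3.1 covers all dose reduction and names another. The tables list different levels below the RDE, and the two sections set different floors. A site can therefore reach two different doses for the same child from the same protocol, and can differ on whether a child who needs less than 200 mg/m2 may continue or must stop.

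A second gap does not depend on the DLT text. Table 6-4 applies to every treated patient, but the only table that Section 6.3.1 gives for its steps starts at the RDE. A patient assigned another level has no stated starting row.

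The statistical consequence is in the tolerability summaries. Protocol Section 10.7.1.6 and SAP Section 2.4.1 summarise dose reductions and relative dose intensity. If two patients at the same dose with the same event were reduced under different tables, each counts as one reduction, but the sizes differ. The summary would then partly reflect which table was read.

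**Working it through.** **Inputs.** Table 6-1 levels and Table 6-3 steps as above. The dose in mg is the level times BSA, rounded to the nearest 50 mg (Section 6.1.1). The minimum reduction after a DLT is 50 mg (Section 6.2.4). The lowest eligible BSA is 0.35 m2 (exclusion criterion 4). The upper end of 2.00 m2, the 0.01 m2 steps and rounding ties up are assumptions; the documents give no BSA distribution.

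**The plan's own figures.** Table 6-1's stated steps reproduce: 200/300 is a 33.3% reduction, 450/300 a 50.0% increase, 560/450 24.4%, 700/560 25.0%, 875/700 25.0% and 1090/875 24.6%. These agree with the stated 33%, 50% and 25% after rounding.

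**First listed level below the current dose (mg/m2).**

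| Current dose | Table 6-1 | Table 6-3 |
|---|---|---|
| 500 fed (RDE) | 450 | 400 |
| 510 fasted (RDE) | 450 | 400 |
| 560 fasted | 450 | no starting row |
| 450 fasted | 300 | no starting row |
| 400 or 320 fed | 300, but no fed levels listed | no starting row; 300 is the highest listed lower level |
| 300 fasted | 200 | no starting row; 200 is the next listed level |

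From the RDE the full sequences are 500/510, 450, 300, 200 and 500/510, 400, 300, 200. Only the first step differs.

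**Size of the first step.** From 510: 1 − 450/510 = 11.8%, against 1 − 400/510 = 21.6%. From 500: 10% against 20%.

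**In mg.** At BSA 1.0 m2 the starting dose is 500 mg, falling to 450 or 400 mg. At BSA 1.5 m2 it is 750 mg, falling to 700 or 600 mg. At BSA 0.5 m2 the starting dose is 250 mg. There 450 mg/m2 also rounds to 250 mg, so the 50 mg minimum makes it 200 mg, the same as the Table 6-3 step.

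**Over the BSA grid.** The grid has (2.00 − 0.35)/0.01 + 1 = 166 values. The reduced dose is the smaller of the rounded new dose and the current rounded dose minus 50 mg.

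- From 500, the two tables give different mg doses at 128 of 166 values (77%).
- From 510, they differ at 132 of 166 (80%).
- Without the 50 mg minimum, they differ at 144 of 166 (87%). That figure should not be used for a DLT, because Section 6.2.4 imposes the minimum.

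**Floor.** Section 6.2.4 gives 150 mg/m2 and Table 6-3 gives 200 mg/m2. The lowest level in both tables is 200, so 150 is a row in neither.

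**The case against.** The strongest case on the other side has four parts.

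1. Section 6.2.4 does not prescribe a one-level step. It asks for a lower level judged safe, at least 50 mg lower. A reader might infer that the same one-level instruction after a DLT gives two doses; for that section the text does not support this. The 450 figure is read from a table that has no 500 or 510 row and calls itself an example. This stands and limits the claim to a difference in listed levels.

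2. At the RDE both sections can be followed at once. Moving from 510 to 400 mg/m2 is a reduction of at least 50 mg at 165 of the 166 grid values (all but 0.44 m2). This also stands. It shows that one reading satisfies both texts, but a site that follows the table named in the DLT text is not told to prefer that reading.

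3. A reader might infer that the two tables divide the cases, one for DLTs and the other for everything else, or that a patient assigned 450 faces 300 in one table and 400 in the other. Neither is supported. Section 6.3.1 has no DLT exception, so the sections overlap, and Table 6-3 has no step for a 450 start. The finding there is that the step is undefined.

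4. Little can still change. By Amendment 8 recruitment had closed, all patients were reported to have completed at least 6 cycles, and DLTs are limited to the first 21 days. The SAP already lists all doses with reasons for change (Section 2.4.1) and derives reductions from the dose actually taken (Section 5.3). This stands for new DLTs. It does not cover Table 6-4 reductions in the twelve patients still on treatment, although the documents do not show whether any of them started below or above the RDE. Nor does it help in reading reductions already made.

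**Conclusion.** The concern holds in a limited form. Two sections that both apply to a DLT name different tables, and no text gives precedence. From the RDE the first listed lower level is 450 or 400 mg/m2, and the later levels agree. Under the assumed BSA grid and with the 50 mg minimum, the resulting doses differ at 128 or 132 of 166 values. Those counts weight every BSA value equally and are not the share of patients affected. They also rest on taking the highest listed level below the current dose, which Section 6.2.4 does not require.

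Two parts need no such assumption. One dose level is undefined for patients who did not start at the RDE, and the floors of 150 and 200 mg/m2 contradict each other. Determination of the maximum tolerated dose is not affected by this point. The live reach is Table 6-4 reductions in patients still on treatment and the interpretation of the dose-reduction and dose-intensity summaries in the final report.

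**What to change.** Reconcile Section 6.2.4 (dose modification related to DLTs), Section 6.3.1 including its QTc paragraph, Table 6-1 and Table 6-3. One reference should define a dose level for every assigned dose and regimen, and one floor should apply, both after a DLT and after other toxicity. Which levels and which floor apply is for the sponsor's clinical team to decide.

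In the SAP, have the dose listing already planned in Section 2.4.1 show mg/m2 before and after each reduction, so that reductions made under different tables can be told apart. The cost is a short protocol clarification and one added item in an existing listing, with no new data collection.
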